# 7.8.11 Subsequent Anti-Cancer Therapies and Procedures

Subsequent anti-cancer therapies and procedures will be collected throughout weeks 0-12 treatment visits as well as long-term treatment and follow-up visits. The following will be summarized by treatment arm in safety analysis set and will be presented in a listing.

- Any subsequent anti-cancer therapy
- Type of therapy
- Number of lines of therapy

Line of therapy will be reviewed and assigned by medical monitor. For first line, second line and third line treatment, number of subsequent chemotherapy agents and number of patients in each chemotherapy regimen/agents, best response of chemotherapy and reason for discontinuation of chemotherapy will be summarized in each line.

Subsequent procedures will be presented in a separate listing.

# 7.9 Multiplicity

Where possible, parameters will be quantified for direct comparisons between the treatment arms. Since the sample size is not based upon a hypothesis to be tested regarding the differences in primary and secondary endpoints between treatment arms, the statistical analyses to compare differences in parameters between treatment arms should be considered exploratory. All other statistical tests (where performed) will be two-sided and tested at the alpha=0.05 level of significance; all these p-values produced should be deemed descriptive. There will be no adjustment to multiplicity.

# 7.10 Interim Analyses and Data Monitoring

An exploratory analysis of the PFR at 6 months after treatment initiation will be used as a nonbinding futility analysis for each treatment arm. Upon obtaining the progression status after 6 months on study from the first 36 (18 per arm) and subsequently from all enrolled patients, interim analyses will be performed and presented to the DMC, which will include estimates of PFS and assessment of PFR. Based on the assumptions in Protocol Section 10.3, futility guidelines at Stage 1 will be based on 18 patients and will require at least 6 patients to be progression free to continue on to Stage 2.

For the purposes of safety monitoring, key safety analysis will also be performed quarterly. The DMC will evaluate the available data and make necessary recommendations to the study. Details will be outlined in the DMC charter

# 8 CHANGES FROM THE PROTOCOL SPECIFIED STATISTICAL ANALYSES

If discrepancies exist between the text of the statistical analysis as planned in the protocol, and the final SAP, a protocol amendment will not be issued, and the SAP will prevail.

# Appendix 1: NCI CTCAE V4.03 Grades for Laboratory Parameters

## **Panel: Chemistry**

Lab Test	Unit	Grade 1	Grade 2	Grade 3	Grade 4
Albumin	g/L	[30, LLN)	[20, 30)	[0, 20)	Life-threatening consequences; urgent intervention indicated
Alkaline Phosphatase	U/L	(ULN, 2.5*ULN]	(2.5*ULN, 5*ULN]	(5*ULN, 20*ULN]	>20*ULN
ALT (increased)	U/L	(ULN, 3.0*ULN]	(3.0*ULN, 5.0*ULN]	(5*ULN, 20*ULN];	>20*ULN
AST (increased)	U/L	(ULN, 3.0*ULN]	(3.0*ULN, 5.0*ULN]	(5*ULN, 20*ULN];	>20*ULN
Bilirubin	umol/L	(ULN, 1.5*ULN]	(1.5*ULN, 3*ULN]	(3*ULN, 10*ULN]	>10*ULN
Calcium high (Hypercalcemia)	mmol/L	(ULN, 2.9]	(2.9, 3.1]	(3.1, 3.4]	>3.4
Calcium low (Hypocalcemia)	mmol/L	[2.0, LLN)	[1.75, 2.0)	[1.5, 1.75); hospitalization indicated	[0, 1.5); life threatening consequences
Creatinine (increased)	umol/L	(1 – 1.5*baseline]; (ULN, 1.5*ULN]	(1.5 – 3.0* baseline]; (1.5*ULN, 3*ULN]	>3.0*baseline; (3*ULN, 6*ULN]	>6*ULN
Glucose high (hyperglycemia)	mmol/L	(ULN, 8.9]	(8.9, 13.9]	(13.9, 27.8]; hospitalization indicated	>27.8; life threatening consequences
Glucose low (hypoglycemia)	mmol/L	[3.0, LLN)	[2.2, 3.0)	[1.7, 2.2)	[0, 1.7); life threatening consequences; seizures
Potassium high (hyperkalemia)	mmol/L	(ULN, 5.5]	(5.5, 6]	(6, 7]; hospitalization indicated	>7; life-threatening consequences
Potassium low (hypokalemia)	mmol/L	[3, LLN)	[3, LLN); symptomatic; intervention indicated	[2.5, 3) ; hospitalization indicated	[0, 2.5); life- threatening consequences
Sodium high (hypernatraemia)	mmol/L	(ULN, 150]	(150, 155]	(155, 160]; hospitalization indicated	>160; life- threatening consequences
Sodium low (hyponatraemia)	mmol/L	[130, LLN)	UNDEFINED	[120, 130)	[0, 120); life- threatening consequences

Lab Test	Unit	Grade 1	Grade 2	Grade 3	Grade 4
Hemoglobin	g/L	[100, LLN)	[80, 100)	[0, 80);	Life-threatening
(decreased)	-			transfusion	consequences; urgent
				indicated	intervention indicated
Platelet count	10^9/L	[75, LLN)	[50, 75)	[25, 50)	[0, 25)
(decreased)					
WBC (decreased)	10^9/L	[3, LLN)	[2, 3)	[1, 2)	[0, 1)
Lymphocytes	10^9/L	[0.8, LLN)	[0.5, 0.8)	[0.2, 0.5)	[0, 0.2)
(decreased)		- ,			- ,
Neutrophil count	10^9/L	[1.5, LLN)	[1, 1.5)	[0.5, 1)	[0, 0.5)
(decreased)					
Activated Partial	sec	(ULN,	(1.5*ULN,	>2.5*ULN;	
Thromboplastin		1.5*ULN]	2.5*ULN]	hemorrhage	
Time				_	
Prothrombin Intl.	Ratio	(ULN,	(1.5*ULN,	>2.5*ULN; >2.5	
Normalized Ratio		1.5*ULN]; >1 -	2.5*ULN]; >1.5 -	times above	
		1.5 times above	2.5 times above	baseline if on	
		baseline if on	baseline if on	anticoagulation	
		anticoagulation	anticoagulation		

# **Panel: Hematology**

# Reference:

http://evs.nci.nih.gov/ftp1/CTCAE/CTCAE\_4.03\_2010-06-14\_QuickReference\_5x7.pdf

# Appendix 2: SAS Code for Statistical Analyses

Test	Table/Figure	SAS Codes
95% Clopper-Pearson confidence interval	Tumor response based on irRC	<pre>ods listing close; proc freq data = xx; ods output BinomialCLs=CI BinomialProp=prop; table resp / binomial (level = 1 exact) out=freq1 (keep=objresp count); by trt; run; ods listing; **where resp = best overall response trt = treatment arm;</pre>
Median (and 95% CI) for Kaplan-Meier curve	Progression-free survival, Duration of Response	<pre>proc lifetest data=xx method=km plots=(s); time pfs*status (1); strata trt; run; **where pfs = time to event. status: 1=censoring; 0=event trt = treatment arm;</pre>
Hazard ratio, 95% CI, p- value based on a 2-sided stratified log-rank test	Progression-free survival, OS	Proc phreg; (Stratified) model time*status (1) = treat; strata disease_type; Run;
Hazard ratio, 95% CI, p- value based on a 2-sided unstratified log-rank test	Progression-free survival, OS	Proc phreg; (Unstratified) model time*status (1) = treat; Run;

The following table presents the SAS code for the analyses.

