# **4 SAMPLE SIZE DETERMINATION**

Sample size was calculated using a Simon 2-stage design, assuming an unacceptable progression-free survival rate (PFR) of 25% and an acceptable PFR of 45% at 6 months, corresponding to an unacceptable and desirable median PFS of 3 months and 5.2 months, respectively and an exponential survival distribution, 40 patients in each arm (alpha=0.1, beta=0.15) were required. For this study, two groups of up to 40 patients each (up to 80 patients) were to be dosed with CMB305 with atezolizumab or with atezolizumab alone to assess PFS at 6 months and median of PFS with 95% CIs. If favorable results are observed, the study may be expanded to improve the estimates of PFS.

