# 5.1.3.2 Overall Response Rate (ORR) and Duration of Response (DOR)

Overall response rate (ORR) will be defined as the number of patients whose best overall response is complete response (irCR) or partial response (irPR) divided by the number of evaluable patients. Overall response rate based on unconfirmed response and confirmed response will both be summarized.

Duration of response (DOR) will be defined only for the patients whose confirmed best response is irCR or irPR as the time interval between the date of the earliest qualifying confirmed response and the date of progressive disease (PD) or death for any cause, whichever occurs first. DOR in months will be calculated as: (date of PD or death, whichever occurs first – date of first confirmed irCR or irPR + 1)/30.4375.

For patients who are alive without documentation of disease progression following the qualifying response, duration of response will be censored following the same rule defined for PFS.

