# 7.6.3.2 Overall Response Rate (ORR) and Duration of Response (DOR)

ORR will be estimated using the ITT set and EE set will be provided along with their corresponding 2-sided the 95% exact CI using Clopper-Pearson method. Best Overall Response (CR, PR, SD, PD and not evaluable) will be tabulated with 2-sided 95% CI in the same table.

ORR will be compared between treatment arms using a logistic regression. Logistic regression will be performed with the treatment arm and stratification factor of disease type as independent variables.

Lesion assessment (lesion type, organ site, evaluation method, diameter, lesion status and overall response) at each visit will be presented in a data listing.

Median DOR with the corresponding 95% CI will be estimated using the Kaplan-Meier method in each treatment arm. The Kaplan-Meier plots will be displayed.

DOR data will be presented in a data listing.

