# 7.6.3.3 Clinical Benefit Rate (CBR) and Duration of Clinical Benefit

CBR and Duration of clinical benefit will be analyzed using the same methods described for ORR and DOR.

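### As written, the SAP Appendix 2 Clopper-Pearson code does not produce ORR as SAP 5.1.3.2 defines it, and it can pick a different response category in each arm

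*SAP*

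**What the plan says.** SAP 5.1.3.2 sets the endpoint, with evaluable patients as the denominator: "Overall response rate (ORR) will be defined as the number of patients whose best overall response is complete response (irCR) or partial response (irPR) divided". SAP 7.6.3.2 asks for ORR in the ITT and EE sets with a "2-sided the 95% exact CI using Clopper-Pearson method". It adds a second request: "Best Overall Response (CR, PR, SD, PD and not evaluable) will be tabulated with 2-sided 95% CI in the same table".

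The only code for the exact interval is in SAP Appendix 2, in the row for tumour response under irRC: "table resp / binomial (level = 1 exact) out=freq1 (keep=objresp count", with BY processing on treatment arm. The comment beneath it reads "where resp = best overall response trt = treatment arm". The code has no ORDER= option, no format and no step that pools CR with PR. The variable in the KEEP list, objresp, is not the variable tabulated.

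SAP 7.6.3.3 carries the method to the next endpoint: "CBR and Duration of clinical benefit will be analyzed using the same methods described for ORR and DOR". SAP 5.1.3.3 defines CBR by pooling irCR, irPR and irSD.

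**The concern.** ORR is a pooled proportion, but the code takes one level of a variable that its own comment describes as unpooled. Within the five categories of SAP 7.6.3.2, no single level equals CR plus PR. That is so whether level = 1 is read as the first level or as the value 1.

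SAS behaviour adds to the problem. An unquoted number in LEVEL= is a position in the displayed order, and the default order is ascending internal value. With BY processing, only levels present in that arm are counted. The category returned therefore depends on the coding of resp and on which categories happen to occur in each arm. This is general knowledge of the software named in SAP section 1 (SAS 9.4), not something the documents state.

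At stake is a response rate and interval that describe another category, or two different categories set side by side as if they were a comparison. The run need not stop with an error. The same applies to CBR.

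**Working it through.** The documents give no assumed ORR and no ORR-based sample size, so there is no planned figure to reproduce. The check traces which level the code selects and compares it with CR plus PR.

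**Inputs.** From the documents: n = 40 per arm (SAP section 4, "two groups of up to 40 patients each (up to 80 patients"), a two-sided 95% exact interval, five response categories, and levels found separately by arm. Assumed for illustration, because the documents do not give them: the response counts and six possible codings of resp.

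- Arm A: CR 1, PR 3, SD 18, PD 16, NE 2
- Arm B: CR 0, PR 2, SD 18, PD 20, NE 0
- Arm C: CR 0, PR 0, SD 20, PD 18, NE 2

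**Formula.** For x of n, the lower limit is the 0.025 quantile of Beta(x, n − x + 1) and the upper limit is the 0.975 quantile of Beta(x + 1, n − x). The lower limit is 0 when x = 0 and the upper limit is 100% when x = n.

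**Intended ORR (CR + PR).**

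- A: (1 + 3)/40 = 10.0% (2.8 to 23.7%)
- B: (0 + 2)/40 = 5.0% (0.6 to 16.9%)
- C: 0/40 = 0% (0 to 8.8%)

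**What level = 1 returns.**

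| Coding of resp | Arm A | Arm B | Arm C |
|---|---|---|---|
| Text CR, PR, SD, PD, NE | CR, 1/40 = 2.5% | PD, 20/40 = 50.0% | NE, 2/40 = 5.0% |
| Text irCR, irPR, irSD, irPD, NE | NE, 2/40 = 5.0% | irPD, 20/40 = 50.0% | NE, 2/40 = 5.0% |
| Numeric 1 = CR to 5 = NE | CR, 1/40 = 2.5% | PR, 2/40 = 5.0% | SD, 20/40 = 50.0% |
| Flag 0/1, 1 = responder | non-responders, 36/40 = 90.0% | non-responders, 38/40 = 95.0% | non-responders, 40/40 = 100% |
| Flag N/Y | as 0/1 | as 0/1 | as 0/1 |
| Flag 1 = responder, 2 = non-responder | responders, 4/40 = 10.0% | responders, 2/40 = 5.0% | non-responders, 40/40 = 100% |

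Exact limits for the selected levels: 1/40, 0.1 to 13.2%; 2/40, 0.6 to 16.9%; 20/40, 33.8 to 66.2%; 36/40, 76.3 to 97.2%; 38/40, 83.1 to 99.4%; 40/40, 91.2 to 100%.

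Five of the six codings mis-state ORR in arm A, arm B or both. The numeric coding is right in arm B only because that arm has no CR. The responder-first flag is right in A and B and fails in C.

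**How likely is an arm with no responder?** The chance of 0 of 40 is (1 − p)^40. For an assumed true ORR of 5% it is 0.95^40 = 0.129; for 2.5% it is 0.975^40 = 0.363. Both rates are assumptions.

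**The case against.** The strongest reply is that this is schematic code with an unfinished rename. The dataset is a placeholder. SAP section 1 leaves variable mapping to ADaM specifications that are not part of these documents. The name objresp suggests a responder flag was meant, and the logistic regression of ORR in SAP 7.6.3.2 needs a binary outcome. The row is labelled for tumour response in general, so it could also serve the per-category intervals promised for the same table. A gross error, such as an ORR of 90% beside four responders, would show in that table. ORR and CBR are exploratory, between-arm comparisons are exploratory under SAP 7.9, and the futility rule in SAP 7.10 uses PFR.

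Most of this stands, and it limits both certainty and weight. A reader might infer that the reported ORR is bound to describe the wrong category, or that the sponsor means to report CR alone. The documents support neither, because the coding of resp is not given and the definition in SAP 5.1.3.2 is clear.

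It does not rescue the code. If a flag was meant, 0/1 or N/Y coding returns non-responders, and 1/2 coding fails in an arm without responders. If the row is for per-category intervals, a fixed level position by arm does not name a category, and ORR is left with no code. Nor is the appendix mere decoration: it is presented as the code for the analyses, and SAP section 1 requires departures from the plan to be justified and recorded in the study report. Some errors would not look odd either, such as 2.5% or 5.0% in place of 10.0%.

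**Conclusion.** The point holds in this form: followed as written, the Appendix 2 code does not give ORR as SAP 5.1.3.2 defines it, and it can return different categories in the two arms. None of the six codings examined is correct for all three illustrative arms. With those assumed counts, a true 10.0% could appear as 2.5%, 5.0% or 90.0%, a true 5.0% as 50.0% or 95.0%, and a true 0% as 5.0%, 50.0% or 100%.

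This rests on the comment's definition of resp, on PROC FREQ's positional reading of an unquoted level, and on invented counts at n = 40. It does not establish that any reported ORR will be wrong. The actual error, if any, depends on a coding that the documents do not show. The OS and PFS analyses use other code and are unaffected, as are the futility rules. It should be corrected because the stated method conflicts with the stated endpoint, but no trial decision depends on it.

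**What to change.** In Appendix 2:

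1. Derive objresp = 1 if best overall response is irCR or irPR, else 0. Do this within the denominator that the SAP specifies for each analysis: evaluable patients under 5.1.3.2, and the ITT and EE sets under 7.6.3.2. The zero code must not bring patients into a denominator that excludes them.
2. Tabulate that flag and name its level explicitly: `tables objresp / binomial(level='1' exact) out=freq1(keep=objresp count);`. The tabulated and kept variables then agree.
3. Handle an arm with no responder explicitly, since the responder level is then absent from that BY group. Report 0% with the exact upper limit 1 − 0.025^(1/n), which is 8.8% at n = 40.
4. Repeat for CBR with a flag for irCR, irPR or irSD.

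The cost is a few lines of code and a short note. Design, data collection and the SAP's endpoint definitions do not change.
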